Study Overview: This is a randomized, double-blind inpatient or outpatient human laboratory study. Procedures will be completed as a 7-day inpatient protocol in AUD subjects (N=75) and a 4-day outpatient protocol in an age and gender-matched comparison group of healthy control

(HC) subjects (N=75). On day 1, AUD subjects will be administered an alcohol beverage to control time from last drink before undergoing the first fMRI session. Two hours after alcohol administration, resting-state and alcohol-cued activity will be measured. Following the fMRI session on day 1, all subjects will be randomized to once-daily MIFE or placebo administration. They will also complete cognitive assessment tasks such as the Wisconsin Card Sorting Task (WCST) and two parts of the Wechsler Adult Intelligence Scale-III (WAIS-III), the digit span and the digit symbol substitution tests. They will receive their first medication dose on day 1. Over the next 3 days, AUD participants are monitored as they go through supervised alcohol withdrawal. On day 4, all subjects will complete a second fMRI session to quantify FC changes as a function of alcohol withdrawal and medication administration across key brain regions recently shown to be under GR regulatory control. They will also repeat cognitive assessment tasks. On day 5, AUD subjects complete the Trier Social Stress Test (TSST) followed by the Alcohol Motivated Response (AMR) procedure, during which subjects work for either their preferred alcohol beverage or money. On day 6, AUD subjects will participate in a cumulative alcohol administration procedure during which subjective and physiological responses to alcohol are repeatedly assessed. AUD subjects are discharged on day 7 after completion of the cognitive assessment tasks and a brief intervention. AUD participants are followed for two weeks post discharge. HC participants are followed for one week post second fMRI.

Table 1. Study Day	AUD Procedures	HC Procedures
Pre-admission	Assessment, Medical History, Vital Signs, blood work	Assessment, Medical History, Vital Signs, blood work
Day 1	Updated assessment, blood work, urine pregnancy test; alcohol administration and fMRI session 1 MIFE/placebo randomization and dosing; Cognitive Assessment	Updated assessment, blood work, urine pregnancy test; fMRI session 1 MIFE/placebo randomization and dosing; Cognitive Assessment
CRU stay	Days 2-6: Alcohol withdrawal monitoring	
MIFE/placebo dosing	Days 2-6	Days 2-4

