Daily at 8:00 pm, participants will complete self-reports of alcohol craving, including Visual Analog Scale for alcohol and tobacco craving (VAS); Penn Alcohol Craving Questionnaire (PACS) (Flannery et al., 1999), Beck Depression Inventory-II (BDI-II), Beck Anxiety Inventory (BAI), Obsessive Compulsive Drinking Scale (OCDS), and Alcohol Urge Questionnaire (AUQ). Nursing staff will complete clinician-administered instruments for alcohol withdrawal assessment (see below). Participants will have PRN access to over the counter medications to treat headache, gastrointestinal upset and body aches.

Each day of the CRU stay, the CRU nurse will administer the Systematic Assessment for Treatment of Emergent Events (SAFTEE) (Johnson et al., 2005). This standardized, structured

instrument is specifically adapted for use in substance use disorder clinical trials, to collect information on incidence and severity of medication side effects and adverse events.

To determine if the degree of elevation of CORT in response to GR blockade by MIFE correlates with any of our outcome measures, each morning upon wakening and at bedtime on the CRU, a salivary cortisol sample is obtained. Baseline samples will be collected on day 1, prior to beginning study medications. Measurement of CORT in saliva is not invasive and multiple samples per day are easily obtained. Unlike serum CORT, salivary CORT is unbound to protein and reflects the physiologically relevant fraction. For each sample, subjects chew a pad for 90 sec, which they then place into a capped salivette. Saliva is harvested by centrifugation and stored in a cryotube at -70 until assayed in duplicate (Diagnostic Systems Laboratories; Webster, Texas). The intra- and inter-assay coefficients of variation are below 5%. As we expect variability in CORT within and across MIFE doses, these data will be included in our analyses.

Because MIFE is occasionally associated with hypokalemia, serum potassium level is obtained before study procedures on day 1 and again on day 7 and at the 1 week follow-up visit. Potassium replacement will be addressed as needed.

Outpatient procedures for HC: Healthy control subjects will complete the study as a 4-day outpatient protocol.

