MIFE has a rapid onset of action and achieves peak plasma levels within 1 - 2 hrs of oral dosing. Peak plasma levels and bioavailability increase as a function of dose but are not directly proportional to dose. However, plasma concentrations of MIFE metabolites do increase in direct proportion to dose; metabolites have antiglucocorticoid activity and contribute to long-acting drug effects (Pomara et al., 2002). MIFE is effective with once-a-day dosing. The half-life is 40 hrs following a single dose and 84.6 hrs following multiple doses. Following discontinuation of MIFE, plasma levels are detectable for up to 2 weeks (Heikinheimo et al., 2003). For this study, we selected to use the high MIFE dose of 1200mg, based on recent clinical trials for other neuropsychiatric disorders associated with HPA-axis dysfunction, and that 1200 mg MIFE has been safely administered over extended periods (MIFE Investigator Brochure, Corcept Therapeutics). This study only exposes subjects to MIFE for up to 6 days. We are not planning to reduce MIFE dose during such a brief treatment period. If a subject experiences significant medication side-effects or any serious adverse event or if the participant declines to continue medication, then we will discontinue that participant from the study. It

should be noted that inpatient subjects are under continuous nursing observation throughout the CRU stay and thus adverse events can be identified and addressed rapidly. HC subjects will be instructed to call the study doctor if they have any adverse events. Subjects will be randomized to active MIFE and placebo on a 2:1 ratio.

In the proposed study, MIFE will be administered under an IND ([name] 124365). MIFE (300 mg) and matching placebo will be provided by Corcept Therapeutics, Menlo Park, CA. We will overencapsulate the medication and placebo as necessary. The Johns Hopkins Bayview Investigational Drug Services (IDS) will maintain the inventory and dispense the medication. MIFE absorption and elimination are not affected by age, body weight, BMI, race or sex (Mifepristone Investigator Brochure, Corcept Therapeutics).

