Since MIFE has potent antiprogestational effects, women participants will undergo a urine pregnancy test at the time of the initial alcohol sensitivity and prior to the first MIFE dose. On day 1, participants will be dosed after the fMRI session under nursing observation. On all subsequent days, inpatient participants will be dosed once daily at 9 am under nursing observation and HC outpatient participants will be given take home medication and asked to take the medication under nursing observation via video teleconference. Blood draws for MIFE trough and peak plasma level determinations will be drawn at 15 minutes before dosing and 90 minutes after dosing, respectively. MIFE blood draws will be completed for outpatient HC participants on day 4 only. Subjects can discontinue taking study medication at any time, ending study participation. Discontinued subjects will be asked to complete post-discharge follow up.

fMRI scans for functional connectivity and alcohol cue activation on Days 1 and 4: Both AUD and HC participants undergo fMRI sessions. On day 1, all subjects report to the IPSAR office at 9 am, complete interim assessment procedures, urine drug and pregnancy screens and receive a calorie-controlled breakfast. AUD and HC smokers with tobacco use disorder (TUD) will receive a nicotine patch (21mg). At 10 am on day 1 only, AUD subjects will receive an alcohol drink in a standardized calorie-free mixer targeting a blood alcohol level of 80mg% based on gender and BMI. We have included this drink for several reasons. Most importantly, we want to standardize time from last drink to start of scanning across AUD subjects, since subjects will come for admission with varying abstinence durations. Secondly, we want to minimize the impact of both alcohol intoxication and withdrawal on this initial scan, and so have attempted to time the scan to begin when BAL is at or near 0mg%. Finally, we anticipate that this pre-scan drink will act as a primer for the alcohol cuing procedure employed in the study. At 1 pm, all subjects undergo rs-FC and CA fMRI procedures.

fMRI Scanning procedures: All studies will be conducted at 3T in the F.M.Kirby Research Center for Functional Brain Imaging. We will follow all COVID-related safety procedures implemented by the Kirby Research Center. We will counter-balance for handedness and always use the right hand for responses.

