This study will include two groups of participants – persons with AUD and healthy controls. AUD subjects will have a current DSM 5 alcohol use disorder and will be actively drinking at least 50% above NIAAA recommended guidelines (women >10 drinks/week and men >20 drinks/week) and at least 5 binge drinking episodes in the past 30 days. Recent heavy drinking will be confirmed by PEth blood spot analysis ≥ 50 ng/mL. HC subjects will not meet DSM 5 criteria for AUD and will not be drinking above NIAAA recommended guidelines as confirmed by PEth blood spot analysis < 50 ng/mL. We expect to consent 450 subjects in order to accrue 150 subjects into the study procedures (N=75 for AUD and N=75 healthy controls). Historically, our retention in the CRU has been outstanding, with over 90% of subjects completing the protocol.

Additional Inclusion Criteria for all subjects:

- Nontreatment seeking volunteers;
- 21 – 60 years old;
- English speaking;
- 5th grade literacy to ensure ability to read study assessment instruments;
- no current serious psychiatric or health problems that would contraindicate study participation;
- BMI > 19 and < 40 ; medication dosing is not weight-adjusted. We have restricted the weight range of participants to reduce weight-associated variability;
- For women, negative urine pregnancy test prior to initiating MIFE treatment and agreement to use nonhormonal birth control for 2 weeks following last MIFE dose. A medical record of surgical sterilization or elevated FSH level confirming post-menopausal status is required to document non-childbearing potential;
- No adult seizure history;
- No serious alcohol withdrawal complications in prior alcohol withdrawal episodes;

- Some non-drinking days on 90-day TimeLine Followback Drinking Calendar;
- Study Physician and PI recommendation.

Exclusion criteria for all subjects:

- Women on hormonal birth control, or who are pregnant, nursing or planning pregnancy; women with unexplained vaginal bleeding;
- Current DSM 5 mood, anxiety or psychosis diagnosis or currently treated with psychiatric medication;
- Current substance use disorder except alcohol, marijuana (mild) or tobacco; current illicit drug use other than marijuana;
- History of serious alcohol withdrawal symptoms (e.g., seizures, hallucinations) or history of inpatient, medicated alcohol withdrawal management, and CIWA-Ar score at time of assessment ≥ 12 ;

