Aim 1: CA will be measured from contrasts of parameter estimates derived from event-related analysis. FC will be measured using the peak cross-correlation between seed regions and other ROIs. In both cases, results obtained for each subject can then be used in a second-stage analysis for making population inferences and group comparisons (as was done in Fig 6). For example, the correlation between the resting-state time series from NAcc and the time series from all other brain regions can be used to create a NAcc correlation volume for each subject. Using repeated-measure ANCOVA with between-subject factors of drug group (Placebo, GR antagonist) and alcohol history (AUD, HC) and within-subject factors of time (scan 1, scan 2), differences in these correlation volumes before and after drug treatment can be compared for the medication and AUD vs. HC groups in order to characterize group-dependent differences in altered NAcc connectivity resulting from the medication intervention. Potential confounding factors will be examined and added to the model as covariates if necessary. Multi-linear regression will be used to test the correlation between post-treatment FC and CA with the self-reported alcohol craving and withdrawal measures (VAS, OCDS) in AUD subjects. Finally, we test the correlation between FC and CA dysregulation and alcohol exposure history collected from 90-day Time line follow-back (TLFB). Daily alcohol use data collected from TLFB will be summarized as number of drinking days, number of binge drinking days, and number of drinks

per drinking day for all subjects. Then linear regressions models will be constructed to test the correlation between these drinking measures and FC and CA measures from scan 1.

Aim 2: The main outcomes are CIWA-Ar scores for alcohol withdrawal, VAS and OCDS scores for alcohol craving, and Profile of Mood States 2-Short Version subscale scores. The normality of the measures will be examined first and two sample t-test, or equivalent non-parametric methods will be used to compare outcomes between GR antagonist-treated and placebo-treated groups. We will also use ANCOVA model to adjust for potential confounding factors as covariates.

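### No pre-dose score is scheduled for the AUD craving and mood scales, CIWA-Ar has only a screening score, and the Aim 2 mood scale (POMS 2-Short) has no time point during abstinence

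*Combined protocol and SAP*

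**What the plan says.** All references are to the combined protocol and SAP.

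- **Battery timing (Section 4a, General CRU procedures).** "Daily at 8:00 pm, participants will complete self-reports of alcohol craving". The scales named are VAS, PACS, BDI-II, BAI, OCDS and AUQ. Neither the screening instruments, the updated day 1 assessment (which names only an interim drinking calendar) nor Table 1 lists an earlier run.
- **Day 1 order (Section 4a, Study Overview, MIFE Administration and fMRI scans).** "At 1 pm, all subjects undergo rs-FC and CA fMRI procedures"; "Following the fMRI session on day 1, all subjects will be randomized to once-daily MIFE or placebo administration"; "On day 1, participants will be dosed after the fMRI session under nursing observation". The dose has no clock time. MIFE "achieves peak plasma levels within 1 - 2 hrs of oral dosing".
- **Aim 2 outcomes (Section 7c, Statistical Analyses).** "The main outcomes are CIWA-Ar scores for alcohol withdrawal, VAS and OCDS scores for alcohol craving", together with "Profile of Mood States 2-Short Version subscale scores". The test is a two-sample comparison, followed by ANCOVA for confounders that are not named. The Aim 4 paragraph, by contrast, does mention baseline measures.
- **CIWA-Ar before treatment (Section 5, exclusion criteria).** "CIWA-Ar score at time of assessment ≥ 12" is part of an exclusion, so a screening score exists. During the stay CIWA-Ar is scored every 4 hours while awake, with no pre-dose score specified.
- **A pre-dose baseline in the same section.** General CRU procedures does require salivary cortisol on day 1 before study medication begins.

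**The concern.** Aim 2 is worded as a reduction in craving and an improvement in low mood, and Hypothesis 1b relates brain normalization to the size of craving and withdrawal reductions. Both suggest a starting point. The brain measures have one, at scan 1 before dosing; the self-report scales do not. If the first VAS or OCDS score is taken after the first dose, the arms cannot be compared on pre-treatment craving, the analysis cannot be adjusted for it, and any change computed from that evening would start from a post-randomization value. A pre-dose score cannot be recovered once a subject has been dosed.

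POMS 2-Short has a further gap. It is not in the evening battery, and the only POMS item scheduled is a single subscale (Tension Anxiety) in the day 6 alcohol session. Moving the existing battery earlier would therefore not give Aim 2 a mood measure during abstinence.

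**Working it through.** **1. Schedule check for AUD subjects on day 1** (Section 4a)

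| Time | Event |
|---|---|
| 9 am | Arrival, interim assessment |
| 10 am | Alcohol drink |
| 1 pm | Scan 1 |
| After scan (no clock time) | Randomization, first dose |
| 8 pm | First evening battery |

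Pre-dose administrations listed: VAS 0, OCDS 0, PACS 0, AUQ 0, BDI-II 0, BAI 0, POMS 2-Short 0, CIWA-Ar 1 (at screening). That the dose precedes 8 pm, and that the daily battery begins on day 1, are inferences from the word daily and the 1 pm scan. They are sound, but the text states neither.

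**2. The plan's own Aim 2 figure** (Section 7c, Power analyses)

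Inputs: placebo mean 11.5 (SD 2.1), active mean 9.3 (SD 2.2), alpha 0.05, power above 0.8. Two-sided testing is assumed, since sidedness is not stated.

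- Pooled SD = √((2.1² + 2.2²)/2) = √4.625 = 2.15
- d = (11.5 − 9.3)/2.15 = 1.02
- Two-sample t-test, 1:1: 34 in total gives 80% power and 38 gives 85%. The stated 20 per group gives 88%, which agrees with power above 0.8.

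**3. Power without a baseline at the actual allocation**

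A 2:1 ratio of 75 AUD subjects is 50 versus 25.

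- Noncentrality = d × √(50 × 25/75) = 1.023 × 4.082 = 4.18, on 73 degrees of freedom: power about 98%.
- At half the planned effect (1.1 VAS points, d = 0.51), noncentrality = 2.09: power about 54%.

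**4. What a baseline covariate would add**

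With baseline-outcome correlation r, residual variance is multiplied by (1 − r²), so noncentrality is divided by √(1 − r²). The documents give no r; 0.3 to 0.7 is assumed. The one degree of freedom spent on the covariate is ignored. Detectable difference is at 80% power.

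| r | Variance removed (r²) | Detectable difference, SD | In VAS points (× 2.15) | Power at half the planned effect |
|---|---|---|---|---|
| none | 0% | 0.70 | 1.50 | 54% |
| 0.3 | 9% | 0.66 | 1.43 | 58% |
| 0.5 | 25% | 0.60 | 1.30 | 66% |
| 0.7 | 49% | 0.50 | 1.07 | 82% |

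**5. Chance imbalance that would go unseen**

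SE of the difference in baseline means = √(1/50 + 1/25) = 0.245 SD. The 95% range is ±1.96 × 0.245 = ±0.48 SD. If the baseline SD is also 2.15 (an assumption), that is about ±1.0 VAS point, against a planned difference of 2.2.

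**The case against.** Several points on the other side stand.

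- **A reader might infer that the Aim 2 comparison is biased.** It is not. Hypotheses 2a and 2b are comparisons with placebo, allocation is randomized and blinded, and the first-line test compares outcomes between arms. That is valid without a baseline.
- **A reader might infer that the day 1 evening score will serve as the baseline and absorb early drug effect.** Nothing in the documents plans this. A peak plasma level within 1 to 2 hours also does not show an effect on craving by 8 pm.
- **A reader might infer that no Aim 2 scale is scored before treatment.** CIWA-Ar is, at screening. It is a weak baseline, because eligibility limits it and it is taken before supervised withdrawal, but it exists. BDI-II and BAI are secondary outcomes in Section 7b, not Aim 2 main outcomes in Section 7c.
- **A reader might infer that Hypothesis 1b has no pre-dose craving measure at all.** Subjects rate craving by button press during scan 1, before dosing. That is a different instrument from the VAS and OCDS named in the analysis. The planned regression also uses post-treatment imaging measures and specifies no craving change score, although the hypothesis speaks of reductions.
- **The gain may be small.** Subjects arrive with varying abstinence durations, so a score taken before the 10 am drink may correlate only modestly with evening scores during withdrawal. This is why r = 0.3 is in the range.

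One objection carries less weight: the day 1 updated assessment is not itemized in full and might include these scales. Nothing says so, while the same section does spell out a pre-dose baseline for cortisol. The supportable statement is that no pre-dose run is scheduled, not that none could take place.

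**Conclusion.** The point holds as a gap in the assessment schedule that is cheap to close. It is not a flaw in the validity of the randomized comparison. At the planned effect the trial does not need a baseline for power. The benefit appears if the true effect is well below the one borrowed from the single outside study cited for Aim 2, and its size depends on an assumed correlation. The balance check and the pre-dose starting point for change in Hypothesis 1b do not depend on that assumption; without a pre-dose score on these scales, neither is available. The missing abstinence time point for POMS 2-Short is the more basic omission, since a named main outcome has no scheduled measurement in the period it is meant to describe.

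**What to change.** 1. On day 1, in the 9 am assessment block, before the 10 am drink and before the first dose, have AUD subjects complete the evening battery plus POMS 2-Short. Score CIWA-Ar once as a research baseline, and record time since last drink.
2. Add POMS 2-Short to the 8 pm series, and enter both changes in Table 1.
3. In Section 7c, name the pre-dose score of each scale as the ANCOVA covariate for Aim 2, and as the starting point for change in Hypothesis 1b. Keep the 8 pm scores as outcomes.
4. State a clock time or window for the day 1 dose, so that its order relative to the evening battery is explicit.

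Cost: one extra set of forms and one clinician-rated CIWA-Ar on a visit that already has an assessment block, and one added scale each evening. Subjects already dosed cannot supply the score, so if enrolment has begun the covariate will be missing for them and the analysis text should say how that is handled.
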